B.3. Physical Activity Counseling: Participants meet one-on-one with an exercise physiologist for recommendations for physical activity to improve overall health. Aerobic activity recommendations will be to target at least 6,000 steps per day and five 30- to 35-minute walking sessions per week. Discussions include first, how to assess daily steps and second, to increase daily steps each week until the 6,000 step per day target is reached. Walking will be recommended at a moderate intensity and described as “able to carry on a brief conversation but not able to sing” or as a 12-14 on a 20-point scale of exertion. Resistance training recommendations will be two sessions per week, each separated by 48 hours. Instructions for 8-10 upper and lower body resistance exercises using Thera-bands will be reviewed; Thera-bands and written summaries will be provided.

B.4. Physical Activity Fidelity: Participants be provided with commercial activity monitors and an exercise journal to record daily steps, walking sessions, and resistance sessions. Each week for 16 weeks, activity monitor data will be downloaded for computerized analysis.

B.5. Minimize Attention Bias: Study staff will connect with CHAT participants once a month to ensure they don't have any questions or concerns.

Risk/Benefit Assessment

RISKS:

Blood Draws: There is a risk of local pain, soreness, bleeding, bruising and swelling, as well as light-headedness, dizziness and rarely, fainting and/or a local infection.

Bod Pod: This test may not be comfortable for anyone who has felt claustrophobic (uncomfortable in small places) before but is generally well tolerated.

Pulmonary Function Test: This is a non-invasive procedure. Dizziness during the breathing maneuvers, feeling short of breath, coughing, asthma attack brought on by deep inhalation are possible side effects.

Cardiopulmonary Exercise Test: The risks of the cardiopulmonary exercise test include but are not limited to: fainting, falling, irregular heartbeat, wheezing and shortness of breath, and very rarely, heart

attack or death (less than 1 in 10,000 cases). Participants will be given careful instruction prior to, and during, exercise testing to determine when it is appropriate for them to stop exercising. The exercise test will be performed under the supervision of medical staff who are equipped to deal with emergencies.

NIRS: This is a non-invasive procedure. Site deformation to the skin, redness or bruising may occur momentarily while the cuff is inflated during the assessment.

Exercise Training: Participation in an exercise program may result in muscle, bone and/or joint soreness, discomfort and/or injury.

Mobile Applications: Information collected by mobile applications or 'apps' is subject to their terms of use, which participants should read carefully. Many apps make claims that they are very secure, compliant with federal privacy regulations, and used and tested by other academic centers. However, any mobile app that is downloaded carries potential security risks, and Duke cannot guarantee that these mobile apps are free of risk. Some apps may be able to perform hidden functions or may have security flaws that allow unauthorized access to information. We are unable to fully tell subjects what information these mobile apps are able to access or change on their device (phone/tablet) or what information from their device may be stored outside of Duke. Subjects will be encouraged to limit personal identifiers they enter into mobile applications (particularly their name, date of birth, address, place of employment, and other details that could allow someone to identify them) only to those that they wish to voluntarily share with others. These apps may send/receive information with other mobile apps, including social networking apps or websites (for example, Facebook). If the subject gives permission for this, the terms of use for those apps/websites apply and they should read them carefully.

It is recommended that the subject run a current operating system (OS) on their device, review the privacy/security settings often, and restrict any unnecessary access. These applications may run in the background of their device. Mobile apps may have an unanticipated impact on the operations of their device (e.g., battery drainage). If they do not have an unlimited data/text plan, they may incur additional charges. At the conclusion of the study, we will provide the subject instructions on how to remove the mobile apps from their device or assist them with the process if requested.

We are not asking the subject to make any health decisions based on the use of these mobile apps. The subject will be told to discuss health decisions directly with their healthcare provider.

As with all technology, the subject will be asked to wait until they are in a safe environment, use good judgment and follow prevailing laws. Do not perform study-related activities while they are driving.

In addition to the risks listed above, the subject may experience a previously unknown risk or side effect.

POSSIBLE BENEFITS: We cannot and do not guarantee that a subject will receive any benefit from taking part in this study. Their willingness to take part may, however, increase knowledge regarding the treatment of RA and help future subjects. Several likely benefits include the following:

Subjects will have physical examinations and laboratory tests provided to them at no cost. The study doctor will share with a subject any findings on these tests that indicate a potential problem.

Participants randomized to SWET will receive exercise physiologist-supervised exercise training and

ongoing, dietitian-delivered feedback about diet and weight loss. Participants randomized to CHAT will receive one-on-one counselling about proper diet and exercise recommendations. Upon study completion, CHAT graduates will have the opportunity to join the weekly group nutrition classes in addition to gaining access to the study YouTube exercise channel link; therefore, CHAT graduates will receive the same educational materials as the SWET group upon finishing the study. These benefits are well-recognized as contributing to overall improved health.

WHAT IF THEY CHOOSE NOT TO PARTICIPATE IN THIS STUDY: If a subject does not want to take part in the study, they have the choice to undergo standard treatment for RA. If a subject decides not to take part in this study, their decision will have no effect on the quality of medical care they receive.

Data Analysis & Statistical Considerations

Primary Outcome: Assessing cardiovascular (CV) risk in RA is controversial. Despite general consensus that RA disease activity contributes to CV risk, RA-specific risk calculators perform similar to calculators designed for general populations. Additionally, most calculators use presence or absence of risk factors, which, especially for type 2 diabetes, coronary disease, or tobacco use are unlikely to be reversed in a 12 week non-pharmacologic intervention. Based on this, we elected to exclude those conditions and assess cardiometabolic risk with continuous metabolic syndrome z scores (MSSc). MSSc have accuracy similar to Framingham risk scores and will reflect expected improvements in cardiometabolic variables. MSSc are calculated using differences between Adult Treatment Panel III guideline values and participant values for mean arterial blood pressure, minimal waist circumference, fasting HDL-cholesterol, triglycerides, and glucose with normalization to the cohort standard deviations. We have experience calculating and showing intervention responses with MSSc.

Expected Effect Size and Power: Sample size calculations seen in Table 1 are based on data from our Co-Investigator, [name], work in STRRIDE (Studies of Targeted Risk Reduction Interventions through Defined Exercise), a series of randomized controlled studies of exercise training with and without weight loss in persons at-risk for cardiovascular disease, but without RA.

These data show that relative to a Control group with little change in MSSc, aerobic training and weight loss improve MSSc by -2.5 ± 2.1 . Based on these we would expect similar improvements in our supervised intervention arm (SWET) that includes each of aerobic training, weight loss, and resistance training. Yet, because the SWET 16 week intervention period is on the shorter end of the 16-24 week STRRIDE interventions, full improvements may not be completely achieved. To detect a significant difference between SWET and, the counseling control arm (CHAT) of 1.8, assuming a standard deviation for change of 2.1, 20 persons total will deliver 80% power with a one-tailed alpha of 0.05. We justify a one-tailed test based on our hypothesis that the SWET will significantly exceed CHAT for metabolic syndrome score reduction and that CHAT exceeding SWET, is implausible. Based on our prior experience, we expect an attrition rate of 25% during the intervention period, randomizing a total of 26 RA participants to achieve 20 participants completing the intervention.

Statistical Methods: To assess the difference between SWET and CHAT with respect to the primary and secondary outcomes, we will create change scores (Post-intervention – Pre-intervention) and use linear

models to assess group differences. Distributions will be assessed, and nonparametric methods used or transformations performed if the distribution of the outcomes are non-normal. We will control for important baseline variables, including baseline levels of the outcome of interest. Non-adherent individuals, including those failing to complete the intervention, will be analyzed as specified under an intention-to-treat criterion. Statistical significance will be established as $P<0.05$ (one-tailed) for the primary outcome, MSSc.

Secondary and exploratory outcomes will be tested at $P<0.05$ without Type-I error control for multiple outcomes. When results are reported, we will alert the reader of the P-value issues inherent in the testing multiple of multiple outcomes. This rich database can be used for exploratory analyses, including mediation, moderation, and mechanism; examples include (a) if level of compliance impacts level of change in the CV measures, (b) if change in one CV measure impacts change in other measures (possibly irrespective of group), and (c) interactions. The analyses will proceed chronologically in 4 phases.

Descriptive analyses that will summarize the distribution of the covariates and dependent variables. Bivariate analyses of the association between group membership and the outcome measures. Controlled multivariable analyses, which assess the association between intervention arm and the outcomes controlling for the important covariates – prespecified prior to analysis (see below). Controlled multivariable analyses, which assess the association between outcomes and potential mediators controlling for the important covariates.

Correlation of all outcome changes, which will assess if the intervention has a generalized change across all outcomes, or, is specific to varying outcomes depending on the person. This exploratory analyses may lead to models that predict what kind of person changes in this area but not some other area. While we recognize we have limited power for these exploratory analyses, they may lead to future investigations of individualized prescriptions for weight loss and exercise for certain outcomes. Inclusion of covariates, such as the baseline measure for the outcome of interest, into the models will add precision to the estimates and allow us to assess the generalizability of the effects across the covariates. The list of covariates (i.e. age, race, gender, BMI, disease activity) will be developed prior to any analysis.

Handling of “dropouts”: In addition to intention-to-treat analyses described above, rates of non-adherence and lack of completion will be assessed. The sample that completed versus those that did not will be compared with respect to demographic and clinical differences. These analyses will help improve adherence in future studies as well as to determine any potential impact of dropouts on the findings.

Handling of missing data from participants completing the intervention: Every effort will be made to ensure complete data on all participants. However, occasions arise (e.g. unable to obtain sufficient blood for monocyte functional analyses) where data will be unavailable. Missing data will be assessed for whether it is missing at random, missing completely at random, or missing not at random. For the first two, pair-wise deletion of missing data (If the post-intervention value is missing, the pre-intervention value will be deleted.) will be performed prior to analyses of group differences. If missing

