Weight Loss and Exercise To Improve Rheumatoid Arthritis Cardiovascular Risk

SWET vs CHAT Study

NCT04356183

Document Date: 01/18/2024

Purpose of the Study

Aim 1: To determine if, compared to a counseling health as treatment (CHAT) program consistent with current standard of care, a 16-week supervised weight loss and exercise training (SWET) program improves cardiovascular risk in older, obese persons with RA.

Hypothesis 1a: Compared to CHAT, SWET produces superior improvements in metabolic syndrome (MSSc).

Hypothesis 1b: Compared to CHAT, SWET produces superior improvements in systemic inflammation, RA disease activity and monocyte/macrophage function.

Twenty-six older (ages 60-80 yr.), obese (BMI 28-40 kg/m²) persons with RA (seropositive or erosive) will be randomized to 16 weeks of CHAT or SWET. CHAT is a control arm based on traditional clinical counselling. SWET includes aerobic (3x/w) and resistance (2x/w) training plus a weekly weight loss session. At baseline and post-intervention, comprehensive assessments of “traditional” CV risk will include anthropometrics, blood pressure, body composition, cardiopulmonary exercise tests, and fasting blood for glucose, insulin and lipoprotein profiles. “Inflammatory” CV risk measures will include systemic inflammatory markers, disease activity (DAS-28) and monocyte/macrophage function.

The primary outcome variable is change in a highly validated, continuous z-score for metabolic syndrome (MSSc); MSSc are derived using participants' blood pressure, waist circumference, HDL-cholesterol, triglycerides, and glucose normalized to recommended threshold normative values. With 20 (accounting for 25% attrition) persons total completing both arms, we have 80% power (one-sided) to detect a difference in MSSc change of 1.8 ± 2.1 , where each unit difference in MSSc corresponds to a HR for CV disease of 1.49 (CI 1.37, 1.62).

Aim 2: To determine if, compared to a CHAT program consistent with current standard of care, a 16-week SWET program improves patient-reported outcomes in older, obese persons with RA.

Hypothesis 2: Compared to CHAT, SWET produces superior improvements in self-reported global health, pain, fatigue, and physical function.

Baseline and post-intervention, global health, pain, fatigue, and physical function will be assessed using highly validated measures from the Patient Reported Outcomes Measurement System (PROMIS).

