
Design & Procedures

Study design: Up to 30 adults, may be recruited and enrolled to participate in a cross-sectional study in order to account for screen failures and dropouts during the intervention period. We will stop enrollment after 26 persons have been consented and randomized; the target of 26 persons is to account for attrition after randomization. Occasionally, persons complete the consent process, yet decide not to participate prior to the initial assessments or randomization. We do not consider these persons in our post-randomization attrition calculations.

Our goal is for 20 subjects to complete the study. Subjects 60-80 yrs. of age will be randomized to one of two arms: 1) 16 weeks of a Counseling Health As Treatment (CHAT) program as a control arm designed to reflect traditional clinical counseling or 2) 16 weeks of a Supervised Weight loss and Exercise Training

(SWET) program including supervised aerobic and resistance exercise training plus a weekly weight loss session.

Phone Pre-Screening: Demographics and comorbidities will be assessed via self-report during an initial phone screening interview, with confirmation from the computerized medical record. Once it has been determined that the subject meets pre-screening criteria, they will be scheduled for Visit-1.

Study Schedule

Visit 1 - Consent will last approximately 1.0 hour.

On-site Consent: The consent process will take place in designated research space within the Aesthetics or Stedman buildings located at the Duke Center for Living campus.

Remote Consent: The study informational session is done one-on-one via a scheduled ZOOM meeting appointment with study staff. A secured REDCap platform will be used to obtain the participants' electronic consent (eConsent).

Brief Medical History, including list of medications, and PROMIS questionnaires: After obtaining consent, study staff will provide a link to a REDCap form to capture participant's demographics, medical history and a current medication list. In addition, participants will be asked to fill out some online questionnaires about their overall health, pain, fatigue, physical function, sleep and ability to manage their disease (PROMIS questionnaires). Completion of these measures will likely take between 10 and 12 minutes. Except for global health, scoring is performed by the computerized REDCap interface.

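### The stated 80% power does not follow from the plan's inputs: 20 completers, a difference of 1.8 and an SD of 2.1 give about 58%

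*Combined protocol and SAP*

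**What the plan says.** The power claim appears twice, with the same inputs.

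- Purpose of the Study, Aim 1, counts 20 completers over the two arms together and then claims: "we have 80% power (one-sided) to detect a difference in MSSc change of 1.8 ± 2.1".
- Data Analysis & Statistical Considerations, Expected Effect Size and Power, takes a target of 1.8 for SWET against CHAT and claims: "assuming a standard deviation for change of 2.1, 20 persons total will deliver 80% power with a one-tailed alpha of 0.05".

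Both statements make 20 the total over the two arms and make the target a difference between arms. The Statistical Methods paragraph then plans linear models of change scores comparing the groups, with control for baseline variables, and sets the threshold: "Statistical significance will be established as $P<0.05$ (one-tailed) for the primary outcome, MSSc". Design & Procedures says "Subjects 60-80 yrs. of age will be randomized to one of two arms" and gives no allocation ratio. The plan randomises 26 people so that 20 complete, allowing for 25% attrition.

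**The concern.** A difference of 1.8 with an SD of 2.1 is a standardised effect of 1.8 / 2.1 = 0.857. Ten people per arm is too few to detect that with 80% power in a two-arm comparison, even one-sided. The stated figure therefore looked as if it came from a different calculation.

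This is the only power justification for the only primary outcome. If it is wrong, a non-significant result could be over-read because the trial is described as having 80% power. The protocol also says the trial will supply effect sizes for designing larger studies, so a wrong sample-size statement could be carried into the next design.

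**Working it through.** **Inputs**

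| Input | Value | Source |
|---|---|---|
| Difference between arms in MSSc change | 1.8 | Expected Effect Size and Power; Aim 1 |
| SD of change | 2.1 | same |
| Completers | 20 in total | same |
| Alpha | 0.05, one-sided | Expected Effect Size and Power; Statistical Methods |
| Stated power | 80% | Expected Effect Size and Power; Aim 1 |
| Split | 10 per arm | assumed; any other split of 20 lowers power |

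**Step 1. Try to reproduce the stated 80%.** For a two-sample t-test with n per arm, the noncentrality parameter is (difference / SD) × √(n/2), with 2n − 2 degrees of freedom.

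- Noncentrality: (1.8 / 2.1) × √(10/2) = 0.857 × 2.236 = 1.917.
- One-sided 5% critical value on 18 df: 1.734.
- Power from the noncentral t distribution: **57.9%**. The normal approximation gives 60.7%.

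The risk of missing a true difference of 1.8 is 100 − 57.9 = 42.1%.

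**Step 2. Other readings of the same inputs.**

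| Variant (one-sided 0.05 unless stated) | Power |
|---|---|
| 10 per arm, difference 1.8 | 57.9% |
| 12:8 split | 56.4% |
| 13:7 split | 54.5% |
| 10 per arm, two-sided | 44.2% |
| All 26 with outcomes (13 per arm) | 68.4% |
| 20 per arm instead of 20 in total | 84.5% |
| 10 per arm, difference 2.5 | 82.0% |
| One-sample test, n = 10, difference 1.8 | 80.3% |

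The one-sample result comes closest to the stated figure. Its noncentrality is 0.857 × √10 = 2.711 on 9 df, with critical value 1.833. It tests change within one arm and ignores the variance of the control arm's change. The two-sample result at 2.5 is also near 80%, but 2.5 is the full STRRIDE effect, which the same paragraph says may not be fully reached before it settles on 1.8. Neither is the planned comparison at 1.8.

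**Step 3. What 80% power would require.**

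- At 1.8 and SD 2.1: 17 per arm gives 78.8% and 18 per arm gives 80.9%, so 18 per arm, or 36 completers. With 25% attrition, 36 / 0.75 = 48 randomised.
- At 10 per arm and SD 2.1: a difference of about 2.43.
- At 10 per arm and difference 1.8: an SD of about 1.56.

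**Step 4. Effect of baseline adjustment.** With one covariate correlated r with the change score, the residual SD is 2.1 × √(1 − r²), and the test has 17 df. The text gives no r, so these values are assumptions.

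| Assumed r | Power, 20 completers |
|---|---|
| 0.3 | 61% |
| 0.5 | 68% |
| 0.6 | 74% |
| 0.65 | 78% |
| 0.7 | 82% |

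Power reaches 80% at a residual SD of 1.553, that is r of about 0.67 (R² about 0.45).

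**Step 5. Precision.** The standard error of the difference is 2.1 × √(1/10 + 1/10) = 0.939. The expected two-sided 95% interval is ± 2.101 × 0.939 = ± 1.97 MSSc units. The one-sided 95% bound that matches the plan's test lies 1.734 × 0.939 = 1.63 units from the estimate.

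**The case against.** The arithmetic for the printed inputs is not in dispute. The best case for the plan is that 58% is not the power of the analysis it will run.

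- **Adjustment.** The model controls for baseline MSSc and other variables, and the plan expects this to add precision. That stands as a qualification: 58% is the unadjusted figure and should be labelled so. It does not restore 80%, because the power statement uses only an SD of change of 2.1, and the correlation needed with 20 completers is about 0.67.
- **Intention to treat.** Non-completers are to be included, so up to 26 could contribute. With outcomes on all 26 and one covariate, power would be about 72% at r = 0.3 and 79% at r = 0.5, and would reach 80% near r = 0.52. This is an upper limit, since imputation adds no observed outcomes, and the plan ties its 80% to 20 persons.
- **Table 1.** The power paragraph refers to a Table 1 that is not in the text available for this review. It might name a test or a correlation. The finding is therefore limited to this: the printed sentences give inputs and a result that disagree. The one-sample explanation remains an inference.
- **Interval width.** The ± 1.97 interval is two-sided, whereas the test is one-sided. The matching one-sided distance of 1.63 is below 1.8, so comparing the interval width with the target should not carry the argument.
- **Consequence.** The protocol calls the trial exploratory, and correcting the figure changes no data, test or estimate. However, the plan sets a formal significance threshold for MSSc and claims 80% power in two places, so the figure should be right.

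**Conclusion.** The concern holds. With 20 completers in total, a difference of 1.8, an SD of change of 2.1 and one-sided alpha of 0.05, unadjusted power is 57.9%, about 22 percentage points below the stated 80%. This assumes equal arms, which favours the plan, and a common SD of 2.1 in both arms. At assumed baseline correlations of 0.3 to 0.5, power with 20 completers is 61% to 68%; with outcomes on all 26 and no adjustment it is 68.4%. The claim cannot be supported from the figures the text gives. It must be corrected because it is the sole power justification for the primary outcome.

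**What to change.** Correct the power statement in both places, Purpose of the Study (Aim 1) and Expected Effect Size and Power. Either form will do:

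- With 20 completers (10 per arm), an SD of change of 2.1 and a one-tailed alpha of 0.05, unadjusted power to detect a difference of 1.8 is about 58%.
- With the same numbers, 80% power corresponds to a difference of about 2.4.

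If the sponsor wishes to claim a gain from baseline adjustment, state the assumed correlation and its source beside the adjusted power. Check Table 1 against the corrected text.

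Add one sentence saying that the primary result will be interpreted from the estimate and its confidence interval, and that non-significance does not exclude a 1.8-unit benefit. This goes slightly beyond correcting the number, but it prevents the over-reading described above.

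A note in Design & Procedures dated April 2023 says enrolment is closed, so a larger sample is not proposed. The cost is two reworded sentences, one added sentence and a less favourable stated power. No participant, procedure or test changes.

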Visit 2 - Baseline visit will take place at the Duke Center for Living and will last approximately 2.5 hours. Brief Medical History, including list of medications, and PROMIS questionnaires (If unable to complete prior to Visit 2)

Vitals: Resting Blood Pressure and Heart Rate

Anthropometric Measurements: Height/Weight/Body Mass Index (BMI) calculation

Blood Draw (Fasting)

Physical Examination

Physician RA Joint Assessment: Disease Activity (DAS-28) Assessment

NIRS Muscle Oxidative Capacity Test

Myoton Skeletal Muscle Biomechanical Measurement

Distribute 3-day Food Record

Anthropometric Measurements and Vitals: Anthropometric measurements (Height and Weight) will be obtained and BMI will be calculated. After the subject has relaxed in a seated position for approximately five minutes, resting blood pressure and heart rate will be measured.

Blood Draw: A study nurse will draw up to 150 mL of blood for complete blood count (CBC) with differential and platelet count, erythrocyte sedimentation rate (ESR), high-sensitivity C-reactive protein (hs-CRP), and immune cell function measures. CBC with differential and platelet count is a common

hematology test that is a measure of the number of different cells such as red blood cells, white blood cells, and platelets in the blood. ESR is another common hematology test that is a measure of inflammation. Except for those immune cell function assessments requiring immediate isolation of peripheral blood mononuclear cells, processed blood (plasma) samples will be stored in a -80°F freezer for future assessments of immune cells, inflammation, and cardiovascular risk measures including components of the primary outcome, the metabolic syndrome score. Temporary storage is on the Center for Living Campus with transfer for long-term storage at the Duke Molecular Physiology Institute.

Physician RA Joint Assessment: Disease Activity (DAS-28) Assessment: Participants will receive a 28-joint examination by the study physician to assess RA disease activity and report their overall health assessment. In addition, participants will receive a brief physical examination.

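### The exploratory correlation of outcome changes does not exclude MSSc paired with its own components or specify arm adjustment, so some correlations may not reflect shared response

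*Combined protocol and SAP*

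**What the plan says.** The combined protocol and SAP, under Data Analysis & Statistical Considerations (Statistical Methods), plans a "Correlation of all outcome changes, which will assess if the intervention has a generalized change across all outcomes". The alternative it is meant to separate is that change "is specific to varying outcomes depending on the person". The same section gives as example (b) of the exploratory work the question "if change in one CV measure impacts change in other measures (possibly irrespective of group". No pair of measures is excluded from either analysis, and neither is said to adjust for arm. The section acknowledges limited power and labels this work exploratory.

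The Primary Outcome paragraph computes MSSc from "participant values for mean arterial blood pressure, minimal waist circumference, fasting HDL-cholesterol, triglycerides, and glucose with normalization to the cohort standard deviations". Purpose of the Study, Aim 1, describes the separate traditional cardiovascular-risk assessments as "anthropometrics, blood pressure, body composition, cardiopulmonary exercise tests, and fasting blood for glucose, insulin and lipoprotein profiles". Waist is measured as part of body composition at Visit 3, and HDL-cholesterol and triglycerides fall under the lipoprotein profile, so all five MSSc inputs are also covered as measures in their own right. On the inflammatory side, Aim 1 says that "risk measures will include systemic inflammatory markers, disease activity (DAS-28) and monocyte/macrophage function". The Visit 2 description of DAS-28 is a "28-joint examination by the study physician to assess RA disease activity and report their overall health assessment", and ESR and hs-CRP are drawn at the same visit. The documents give neither a closed list of outcomes nor the DAS-28 formula.

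**The concern.** A correlation between a score and one of its own inputs is partly an identity. It is positive, once the input is oriented so that higher is worse, even when the five inputs change independently of one another. The plan intends to read correlations among changes as evidence about whether response is general or outcome-specific. Pairs of this kind therefore tilt the reading towards general change for a reason unrelated to the intervention or the participants.

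A second route does not involve composites. If participants from both arms are pooled, any two outcomes that SWET shifts will correlate because SWET participants sit on one side of both scales and CHAT participants on the other. That tells us that both outcomes respond on average. It does not tell us whether the same people respond on both, which is what the person-specific branch of the question asks.

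What is at stake is the interpretation of an exploratory analysis that the plan hopes will inform later work on individualized prescriptions. The limited-power statement and the multiplicity warning do not cover this. One concerns missed signals and the other chance findings, whereas this is a bias.

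**Working it through.** The plan gives no figure for the correlation analysis, so there is none to reproduce.

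**Inputs from the plan:** 20 completers; five MSSc components; a planned MSSc difference of 1.8 with SD of change 2.1; a 0.05 threshold for exploratory outcomes.

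**Assumptions:** components enter the matrix; components are equally weighted on a common scale, with independent changes; 10 completers per arm; two-sided tests (the plan does not state sidedness for correlations).

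**Step 1: score against its own component.** For a sum of k standardized components with common correlation ρ, the correlation of one component with the sum is

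r = (1 + (k−1)ρ) / sqrt(k + k(k−1)ρ).

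With k = 5 and ρ = 0, r = 1/sqrt(5) = 0.447. The two-sided 5% critical value at n = 20 is t/sqrt(n − 2 + t²) = 0.444. The expected correlation under no shared response therefore sits at the significance threshold.

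Simulation (40,000 trials, n = 20, independent components):

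| Pair | Mean r | Significant |
|---|---|---|
| Component with MSSc | 0.44 | 53% |
| Component with MSSc minus that component | 0.00 | 5% |
| MSSc with an unrelated outcome | 0.00 | 5% |
| Component with another component | 0.00 | 5% |

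On average 2.6 of the five MSSc–component pairs are significant. At least one is significant in 99% of trials, against 21% after the component is removed from the score. If all 26 randomized participants had data, the critical value would be 0.388 and the 53% would become 65%.

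**Step 2: does unequal weighting remove it?** With independent components of standard deviations s1 to s5 in the sum, component j correlates with the sum at sj / sqrt(s1² + … + s5²). The five squared correlations therefore always add to 1. Unequal weights move the inflation between pairs, but the root mean square stays at sqrt(1/5) = 0.447.

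**Step 3: when the components really do move together.** The component-with-rest correlation is (k−1)ρ / sqrt((k−1) + (k−1)(k−2)ρ).

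| True ρ | Component with MSSc | Component with rest of MSSc |
|---|---|---|
| 0.1 | 0.53 | 0.18 |
| 0.2 | 0.60 | 0.32 |
| 0.3 | 0.66 | 0.44 |

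Real co-movement remains visible after the correction, at a smaller value.

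**Step 4: share of the matrix.** The number of outcomes is not stated. If it is 15, there are 15×14/2 = 105 pairs; if 25, there are 25×24/2 = 300. Five structural pairs are 5/105 = 4.8% or 5/300 = 1.7% of them. They raise the average pairwise correlation by 5×0.447/105 = 0.021 or 5×0.447/300 = 0.007.

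**Step 5: pooling arms.** Take two outcomes that are independent within arm, each shifted by d = 1.8/2.1 = 0.857 SD between equal arms. Pooling adds d²/4 = 0.184 to the covariance and to each variance, so r = 0.184/1.184 = 0.155. Simulation at n = 20 gives a mean of 0.16, with 10% significant. Arm-adjusted residuals return 0.00 and 5%.

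**Step 6: one correction does not do the work of the other.** With every measure shifted by an assumed 0.5 SD and arms pooled, the component-with-rest correlation still averages 0.11 (7% significant). Conversely, arm adjustment leaves the 0.447 of Step 1 untouched, because the overlap exists within each arm.

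**The case against.** The strongest reply is that little of the analysis is touched. A reader might infer that the matrix will show generalized change by construction, and the documents do not support that. Change across all outcomes would have to appear in pairs such as MSSc with PROMIS scores, fitness or macrophage function. These share no component, and Step 1 shows that they are not inflated by overlap. Step 4 shows how small the structural share is. This stands, and it limits the point to the five pairs.

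Other parts of the reply also stand:

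- **Entry of the components is inferred.** There is no closed outcome list, and Aim 1 calls these measures assessments. Their inclusion is the natural reading of a correlation of all outcome changes, but the sponsor may not intend it.
- **DAS-28.** A reader might infer that DAS-28 overlaps with joint counts, self-rated health and inflammation markers as separate outcomes. The documents do not give its formula or say that ESR or CRP enters it. They do not name joint counts or the participant's rating as outcomes, and global health under Hypothesis 2 comes from PROMIS, a separate instrument. Only a conditional point about the marker remains.
- **Pooling is not stated for the correlation step.** Setting group aside is mentioned only in example (b), and only as a possibility. The 0.86 SD shift is planned for MSSc alone.
- **A shared arm effect is relevant to part of the question.** Whether the intervention moves many outcomes is a group-level question, and reporting only arm-adjusted correlations would discard that information. Both kinds should therefore be shown.
- **Direction of harm.** A reader might infer that the overlap would wrongly support individualized prescriptions. Inflation favours the general-change branch, so it works against the person-specific one.

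What does not stand is the suggestion that the exploratory label settles the matter. The analysis as written has no rule that keeps these pairs out, and the label does not tell a reader which correlations are arithmetic.

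**Conclusion.** The concern holds in a limited form and is minor. If the MSSc components enter the matrix, five identifiable pairs carry an expected correlation of about 0.45 with no shared response, and each is significant about 53% of the time at n = 20. This assumes independent changes, equal weights and two-sided testing. Weights change which pairs are most affected but not the overall amount; real correlation among the components raises the uncorrected values further. Pairs without a common component are free of this bias. If arms are pooled, a further correlation of about 0.16 arises between any two outcomes that both shift by 0.86 SD, and less for smaller shifts. The primary MSSc test and the other between-arm comparisons do not depend on this analysis.

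**What to change.** In the correlation paragraph of Statistical Methods, and for example (b):

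- List the variables that enter the matrix.
- Drop each pair of MSSc with its own component, or correlate the component with MSSc rebuilt without it.
- Report arm-adjusted (residual) correlations for the question of whether the same people change across outcomes, alongside any pooled correlations, and label which is which.
- State the DAS-28 version. If it includes ESR or CRP, treat DAS-28 with that marker in the same way. Replacing DAS-28 with joint counts is not needed.

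The cost is a few sentences of SAP text and a few lines of code, with no new data. The downside is that there will be fewer and smaller correlations to report.
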